14.2. EFFICACY ANALYSIS

All efficacy analysis will be presented using the mITT Analysis set. The statistical comparisons described in this SAP for the efficacy variables are exploratory only, and no formal hypotheses testing will be undertaken.

14.2.1 EFFICACY VARIABLES AND DERIVATION

14.2.1.1 MODIFIED RODNAN SKIN SCORE (mRSS)

The mRSS is a validated physical evaluation of participant's skin thickness rated by clinical palpation

Document: \$506df00529e1\$BDE32479744D47F0B3BAA4285D5BE091.docx

Author: [REDACTED]

Version Number: Final v1.1

Version Date: 16Nov2022

Template No.: CS_TP_BS016 Revision 6

Reference: CS_WI_BS005

Effective Date: 02Dec2019

using a 0-3 scale (0 = normal skin; 1 = mild thickness; 2 = moderate thickness with difficulty in making skin folds and no wrinkles; 3 = severe thickness with inability to pinch the skin into a fold) for each of 17 surface anatomic areas of the body: face, anterior chest, abdomen, and with right and left sides of the body separately evaluated, the fingers, forearms, upper arms, thighs, lower legs, dorsum of hands and feet. Individual values are summed and defined as the total skin score. Total score is 0 to 51 with higher scores indicating worse symptomology. Minimally clinically significant difference in mRSS is 3-5 points.¹

14.2.1.2 PERCENT PREDICTED FORCED VITAL CAPACITY (FVC)

Percent predicted FVC is calculated using equations incorporating age, sex, and race. It is calculated as $(\text{FVC Observed} / \text{FVC Predicted}) \times 100$, where FVC predicted is calculated relative to a reference population. Forced expiratory manoeuvres will be performed at least in triplicate with the minimal requirement that three manoeuvres are "acceptable" and that two of these manoeuvres meet end-of-test and repeatability criteria for FVC and forced expiratory volume in 1 second (FEV1).

14.2.1.3 SCLERODERMA HEALTH ASSESSMENT QUESTIONNAIRE-DISABILITY INDEX (SHAQ-DI)

The SHAQ-DI consists of 20 questions referring to eight domains of activity: dressing/grooming, arising, eating, walking, hygiene, reach, grip, and activities. Each item is scored on a 4-point scale from 0 to 3: 0 = without any difficulty; 1 = with some difficulty; 2 = with much difficulty; 3 = unable to do.

The highest (0 is lowest, 3 is highest) score reported by a patient for any individual item in each of the domains is the score for that domain. Additionally, for each category if the patient indicates that they have used an aid or device, then the minimum score for that domain is 2. If the domain is previously scored as 3, then the domain score is 3. For example, if the highest score for dressing/grooming is '1' and the patient says that they use a device for dressing, then the domain score for dressing/grooming would be set to '2'.

The overall composite SHAQ-DI (Standard Disability Index) for a patient is derived as the average of the computed domain scores (where the domain scores are set as described above), with the denominator based on the number of domains in which the patient has provided a response.

The composite score indicates the participant's self-assessed level of disability - higher scores indicate worse symptomology. The outcome is the change in mean score from baseline. A negative change from baseline indicates improvement.

The Scleroderma HAQ (SHAQ) includes an additional five scleroderma-specific visual analogue scales (VAS), addressing overall disease activity, Raynaud's phenomenon, finger ulcers, breathing, and intestinal problems. A composite VAS score is not created nor are the individual VAS scores incorporated into the HAQ DI score.

14.2.1.4 PATIENT GLOBAL ASSESSMENT SCORE

The Patient's Global Assessment represents the patient's overall health status on a 100-mm horizontal

Document: \$506df00529e1\$BDE32479744D47F0B3BAA4285D5BE091.docx

Author: [REDACTED]

Version Number: Final v1.1

Version Date: 16Nov2022

Template No.: CS_TP_BS016 Revision 6

Reference: CS_WI_BS005

Effective Date: 02Dec2019

VAS, ranging from 0 on the extreme left end of the scale indicating "extremely poor health status", and 100 on the extreme right end indicating "excellent health status".

14.2.1.5 PHYSICIAN GLOBAL ASSESSMENT SCORE

The Physician's Global Assessment is to be completed based on examination and overall assessment of the participant. The physician's assessment of the participant's SSc status will be scored on a 100-mm horizontal VAS, ranging from 0 on the extreme left end of the scale indicating "no disease activity" (symptom free), and 100 on the extreme right end indicating "worst imaginable disease activity".

14.2.1.6 COMPOSITE RESPONSE INDEX IN DIFFUSE CUTANEOUS SYSTEMIC SCLEROSIS (CRISS)

The ACR CRISS was developed using expert consensus and data driven approaches for use in clinical trials.^{2,3} The exponential algorithm determines the predicted probability of improvement from baseline, incorporating change in the mRSS, FVC percent predicted, physician and patient global assessments, and HAQ-DI. The outcome is a continuous variable between 0.0 and 1.0 (0 - 100%). A higher score indicates greater improvement.

The application of CRISS algorithm in a randomised clinical trial is a 2-step process.

In the first step, participants will be clinically evaluated to determine whether the participant has improved or not. A participant is considered not improved and is assigned a probability score of improving equal to 0.0, irrespective of improvement on other core items, if he/she develops:

1. New scleroderma renal crisis.
2. Decline in FVC % predicted $\geq 15\%$ (relative), confirmed by another FVC % within a month, high resolution computed tomography (HRCT) to confirm interstitial lung disease (if previous HRCT did not show interstitial lung disease) and FVC % predicted below 80% predicted (attributable to SSc).
3. New onset of left ventricular failure (defined as ejection fraction $\leq 45\%$) or new onset of pulmonary arterial hypertension requiring treatment (attributable to SSc).

If the participant is determined to exhibit improvement in the first step (i.e., not assigned a 0.0), the second step involves computing the predicted probability of improving (a score between 0.0 and 1.0, inclusive) using the equation:

$$\frac{\exp[-5.54 - 0.81 * \Delta MRSS + 0.21 * \Delta FVC\% - 0.40 * \Delta Pt-glob - 0.44 * \Delta MD-glob - 3.41 * \Delta HAQ-DI]}{1 + \exp[-5.54 - 0.81 * \Delta MRSS + 0.21 * \Delta FVC\% - 0.40 * \Delta Pt-glob - 0.44 * \Delta MD-glob - 3.41 * \Delta HAQ-DI]}$$

where $\Delta MRSS$ indicates the change in mRSS from baseline to the visit, ΔFVC denotes the change in FVC % predicted from baseline to the visit, $\Delta Pt-glob$ indicates the change in patient global assessment, $\Delta MD-glob$ denotes the change in physician global assessment, and $\Delta HAQ-DI$ is the change in HAQ-DI. Note that all changes are absolute changes. Additionally, $Pt-glob$ will be calculated as 100-reported score. $\Delta Pt-glob$ and $\Delta MD-glob$ will be divided by 10.

Document: \$506df00529e1\$BDE32479744D47F0B3BAA4285D5BE091.docx

Author: [REDACTED]

Version Number: Final v1.1

Version Date: 16Nov2022

Template No.: CS_TP_BS016 Revision 6

Reference: CS_WI_BS005

Effective Date: 02Dec2019

Participants for which the predicted probability is greater or equal to 0.60 are considered improved, while participants for which the predicted probability is below 0.60 are considered not improved.

14.2.1.7 SCLERODERMA CLINICAL TRIALS CONSORTIUM DAMAGE INDEX (SCTC-DI)

The SCTC-DI is a 23-item composite damage index to quantify organ damage in systemic sclerosis (0-55 scale: >5 moderate damage, >12 severe damage). The total SCTC-DI score is reported on the eCRF.

14.2.1.8 5-D Itch Scale

The 5-D itch scale is a validated brief multidimensional questionnaire designed to be useful as an outcome measure in clinical trials. The five dimensions are degree, duration, direction, disability, and distribution.

14.2.1.9 MISSING DATA METHODS FOR EFFICACY VARIABLE

Missing data will not be imputed, unless otherwise stated.

14.2.1.10 ANALYSIS OF EFFICACY VARIABLES

The observed values and change from baseline values for mRSS, percent predicted FVC, HAQ-DI, patient global assessment score, and physician global assessment score, and SCTC-DI score will be listed for each participant at each protocol specified visit and will be summarised using descriptive statistics over time by treatment group and for all participants.

Actual and change from baseline values will be presented graphically by treatment group using a jitter plot and overlaid box-whisker plot (median, 25th and 75th percentiles) over time.

For mRSS, HAQ-DI, SCTC-DI and 5-D Itch Scale the individual item responses will also be summarised and listed for each participant.

The 5-D itch scale at baseline and at Week 12 will be listed for each participant and will be summarised using descriptive statistics. The change from baseline to Week 12 will also be summarised.

Even though no formal hypothesis testing is planned for this study, exploratory analyses may be performed to assess the treatment effect of FT011 on the efficacy outcomes if data indicates trend and model assumptions hold.

For mRSS, percent predicted FVC, HAQ-DI, patient global assessment score, and physician global assessment score, the change from baseline values will be compared between the FT011 and placebo groups using a mixed model for repeated measures with the baseline value as a covariate, treatment group as fixed effect, the interaction effect between study visit and treatment group, and participant as random effect using an unstructured covariance structure. Parameter estimates will be calculated using restricted maximum likelihood methods (REML), and the Kenward-Rogers method for determining the degrees of freedom. This method will assume that any missing data is Missing at Random (MAR). Example SAS code for the mixed model (using SAS Proc Mixed) is:

Document: \$506df00529e1\$BDE32479744D47F0B3BAA4285D5BE091.docx

Author: ████████████████████

Version Number: Final v1.1

Version Date: 16Nov2022

Template No.: CS_TP_BS016 Revision 6

Reference: CS_WI_BS005

Effective Date: 02Dec2019

```
PROC MIXED data=libname.ADXX REML;  
CLASS TRT01P VISIT SUBJID;  
MODEL AVAL = TRT01P|VISIT BASELINE / DDFM = KENWARDROGER;  
RANDOM VISIT / SUBJECT = SUBJID TYPE = UN;  
LSMEANS TRT01P|VISIT / PDIFF = CONTROL('PLACEBO') CL ;  
RUN;
```

Details of model including covariance structure will be decided based on the model fit. The least squares means, estimated treatment differences (compared to placebo) with two-sided 95% confidence intervals and p-values will be presented.

The CRISS score and SCTC-DI score will be compared between FT011 and placebo group using a Wilcoxon rank-sum test at each post-baseline visit. Example SAS code for this is:

```
PROC NPAR1WAY DATA=LIBNAME.ADXX (where=(trt01p in (placebo treatment_groupX)) WILCOXON;  
CLASS TRT01P;  
VAR AVAL;  
EXACT WILCOXON;  
RUN;
```

The proportions (binary outcomes) of participants showing an:

- improvement in CRISS at Week 12

will be listed, summarised and compared using the Cochran-Mantel-Haenszel test. Example SAS code for the Cochran-Mantel-Haenszel test in SAS Proc Freq is:

```
PROC FREQ DATA=LIBNAME.ADXX;  
TABLES TRT01P*AVAL / CMH;  
RUN;
```

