Confidence intervals will be reported where appropriate. If not mentioned otherwise, all statistical tests will be performed with a type I two-sided error rate of 5%.

Where appropriate, results will be presented graphically. All reported data will be presented in data listing.

The baseline value for each endpoint is defined as the last available, non-missing value obtained prior to the first study medication administration.

The handling of missing data and adjustments for multiplicity will be described in the SAP.

Pharmacokinetic Analyses

All PK analyses will be based on the PK set.

Descriptive statistics by nominal collection time will be presented for the PK concentrations. Concentrations will also be presented graphically on both linear and semi-logarithmic scales.

The PK parameters will be calculated using non-compartmental analysis methods. Full details will be provided in the SAP.

Descriptive statistics will be presented for the PK parameters.

Safety Analyses

All safety analyses will be based on the safety set.

Medical history findings and AEs will be coded by Medical Dictionary for Regulatory Activities (MedDRA) codes and medications the World Health Organisation Drug Dictionary (WHO-DD) Anatomical Therapeutic Chemical (ATC) classification codes.

Treatment-emergent adverse events (TEAEs) are defined as AEs that started or worsen on or after the first study medication administration. The incidence of TEAEs will be summarised by MedDRA terms and treatment group. Drug-related, serious AEs (SAEs) and TEAEs leading to early study withdrawal will also be summarised. Separate summaries will be produced based on severity and relationship to study drug categories.

	
Other safety endpoints including, vital signs, ECGs, safety laboratory results will be analysed descriptively.
 
Efficacy Analyses
 
All efficacy analyses will be based on the mITT set.
 
Descriptive statistics will be presented for all efficacy endpoints and results will be presented graphically where appropriate.
 
Whilst no formal hypothesis testing is planned, exploratory analyses may be performed to assess the treatment effect of FT011 on the efficacy outcomes. Full details of any inferential analyses will be provided in the SAP.

--	---

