#### **12.4.4 Efficacy Analysis**

All efficacy analyses will be based on the mITT set.

Whilst no formal hypothesis testing is planned, exploratory analyses may be performed to assess the treatment effect of FT011 on the efficacy outcomes. Full details of any inferential analyses will be provided in the SAP.

The handling of missing data and adjustments for multiplicity will be described in the SAP.

All collected and derived results will be presented in the data listings.

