##### **12.4.4.1 Continuous Endpoints**

The actual results and the change from baseline values at each post-baseline visit will be summarised by treatment group using descriptive statistics.

The mean change from baseline values ( $\pm$ SD) over time will also be presented graphically.

The change from baseline values will be compared between the FT011 and placebo groups using a mixed model repeated measures model with the baseline value a covariate, treatment group as fixed effect, the interaction effect between study visit and treatment group, and subject as random effect with an unstructured covariance assumption. Parameter estimates will be calculated using restricted maximum likelihood methods, and the Kenward-Rogers method will be used to calculate the degrees of freedom.

The least squares means, estimated treatment differences (compared to placebo) and the corresponding confidence intervals and p-values at each visit will be presented.

The numeric CRIS scores be analysed using a Wilcoxon test.

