##### **12.4.4.2 Binary Endpoints**

Binary endpoints will be summarised using counts, percentages, and odds ratios (compared to placebo). The proportions between each FT011 group and the placebo group will be compared using a Cochran-Mantel-Haenszel test.

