3.3. CHANGES TO ANALYSIS FROM PROTOCOL

There are two planned changes to this SAP that aren't included in protocol:

- 1) The SAP includes the addition of an All Participants Screened Set, which is used for disposition reporting.
- 2) The patient global assessment scores will be inverted for the CRISS calculations. This is described in section 14 of the SAP.

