4.3. FINAL ANALYSIS

All final, planned analysis identified in this SAP will be performed by IQVIA Biostatistics following Certa Therapeutics Pty Ltd authorization of this Statistical Analysis Plan, database lock and determination of analysis sets and unblinding of the study.

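### The SAP makes the exploratory efficacy comparisons depend on an undefined trend in the data; if that condition is applied, comparisons with placebo are reported according to the observed result

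*SAP*

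**What the plan says.** The protocol synopsis reads: "Whilst no formal hypothesis testing is planned, exploratory analyses may be performed to assess the treatment effect of FT011". Protocol 12.4.4 repeats this and adds: "Full details of any inferential analyses will be provided in the SAP". Neither place mentions a trend. The subsections that follow are firm. Protocol 12.4.4.1 states: "The change from baseline values will be compared between the FT011 and placebo groups using a mixed model repeated measures model". Protocol 12.4.4.2 states: "The proportions between each FT011 group and the placebo group will be compared using a Cochran-Mantel-Haenszel test".

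SAP 14.2 sets the status of this work: "The statistical comparisons described in this SAP for the efficacy variables are exploratory only". SAP 14.2.1.10 then adds the condition: "exploratory analyses may be performed to assess the treatment effect of FT011 on the efficacy outcomes if data indicates trend and model assumptions hold". Directly after it, the same section describes three sets of comparisons, all in unconditional terms:

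- a mixed model for five endpoints, with differences, 95% confidence intervals and p-values to be presented;
- Wilcoxon tests for the CRISS and SCTC-DI scores;
- a Cochran-Mantel-Haenszel test for CRISS improvement.

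It also leaves the details of the mixed model, covariance structure included, to be settled by model fit.

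On timing, SAP 4.3 places the final analyses after "database lock and determination of analysis sets and unblinding of the study", and SAP 4.2 plans no interim analysis.

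**The concern.** The condition names no statistic, threshold, direction, endpoint, dose, visit or decision-maker. With no interim analysis and a final analysis that follows unblinding, a treatment trend can only be judged from the by-arm results that the comparison itself would use. SAP 14.2 calls the efficacy comparisons exploratory, so the exploratory analyses in the conditional sentence are most naturally the mixed-model, Wilcoxon and Cochran-Mantel-Haenszel comparisons listed after it.

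Short-term efficacy against placebo is a stated secondary objective. If the condition is used, an endpoint that shows a trend gets a formal comparison and one that does not gets none. The reported set then looks more favourable, or at least more striking, than the full set would. Under Protocol 12, only departures from the SAP have to be presented in the study report. On the conditional reading, a comparison skipped for want of a trend complies with the SAP, so no explanation is required.

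**Working it through.** **The two readings side by side**

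- *Conditional:* the sentence with the trend condition governs the list below it, and comparisons are run after a trend is seen.
- *Unconditional:* the specific statements in SAP 14.2.1.10 and Protocol 12.4.4.1 and 12.4.4.2 govern, and everything listed is run.

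Protocol 12 gives SAP methodology precedence, so the protocol's firm wording does not decide the matter. Within the SAP, both wordings sit in one section. The text is therefore ambiguous, and the calculation below applies only if the condition is used.

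**Inputs**

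- 10 per arm (Protocol 12.1, SAP 3.1) and a two-sided 5% level (SAP 6.1).
- Neither document gives an SD, an effect size or a trend threshold, so results are in SD units and every gate is an assumption.
- Simplification: a single-visit two-sample t-test with 18 df, ignoring repeated measures, baseline adjustment and dropout.

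**How many contrasts the condition could select from** (each dose v placebo)

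- Mixed model: mRSS at 4 visits, and 4 other endpoints at 3 visits: (4 + 4 × 3) × 2 = 32
- Wilcoxon: CRISS at 3 visits, SCTC-DI at 1: (3 + 1) × 2 = 8
- Cochran-Mantel-Haenszel: 1 × 2 = 2
- Total: 32 + 8 + 2 = 42

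**Effect of an assumed gate that favours FT011**

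The standard error of a difference is SD × √(2/10) = 0.447 SD. With no true effect and a gate of one-sided p<g, the share of reported tests with two-sided p<0.05 is 0.025/g. For g = 0.20 this is 0.025/0.20 = 12.5%. Mean reported differences come from simulation, with at least 400,000 trials per scenario.

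| Assumed gate | Share reported, no effect | Mean reported difference, no effect | p<0.05 among reported, no effect | Mean reported difference, true 0.5 SD |
|---|---|---|---|---|
| none | 100% | 0.00 SD | 5.0% | 0.50 SD |
| direction only | 50% | 0.36 SD | 5.0% | 0.61 SD |
| one-sided p<0.30 | 30% | 0.52 SD | 8.3% | 0.71 SD |
| one-sided p<0.20 | 20% | 0.62 SD | 12.5% | 0.78 SD |
| one-sided p<0.10 | 10% | 0.77 SD | 25% | 0.90 SD |

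At a true 0.5 SD the reported mean is about 22% (0.61/0.50) to 80% (0.90/0.50) too large, but confidence-interval coverage stays at 94.1% to 97.1%. With no effect, coverage at the p<0.20 gate is 87.5%.

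**Other assumed gates**

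- Non-directional, two-sided p<0.6, 0.4 or 0.2, no effect: mean bias 0.00 SD; 8.3%, 12.5% or 25% of reported tests have p<0.05.
- Favourable gate judged on another endpoint or visit, no effect: mean 0.18 to 0.39 SD at correlation 0.5, and no bias at correlation 0.

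**What the gate does to the count of significant results** (no effect, all 42 treated as continuous tests)

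- All reported: 42 × 0.05 = 2.1 with p<0.05, of which 42 × 0.025 = 1.05 favour FT011.
- Favourable gate, one-sided p<0.20: 42 × 0.20 = 8.4 reported, of which 42 × 0.025 = 1.05 have p<0.05, all favouring FT011.

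The number of significant results favouring FT011 is 1.05 either way. What changes is what surrounds them.

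**The case against.** The strongest answer is that the condition may never operate. The specific statements that follow it are unconditional, and the sentence can be taken to mean that any comparison that is run will be run as described. SAP 8 also refers to output templates that are not among these documents and may already fix which tables are produced. On that reading, Protocol 12 would require a dropped comparison to be declared. This stands in part: it makes the consequence conditional, but it does not make the wording clear.

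Second, little depends on these comparisons. They are exploratory, the trial was not sized for them and the primary objective is PK. By-arm descriptive summaries are unconditional for the five mixed-model endpoints, SCTC-DI and 5-D Itch, so a crude difference can be rebuilt. A missing comparison can be noticed against the SAP's list. For the 10 Wilcoxon and Cochran-Mantel-Haenszel contrasts the SAP specifies no difference estimate, so the SD figures apply only to the 32 mixed-model contrasts. All of this stands and limits the harm.

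Third, a reader might infer an undeclared change from the protocol, because SAP 3.3 says "There are two planned changes to this SAP" and the trend condition is not one of them. The documents do not support resting the point on this: Protocol 12.4.4 already uses permissive wording and hands the inferential detail to the SAP, whose methodology takes precedence.

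A reader might also set 12.5% against 5% and infer more false positives. That is not so. The 12.5% is a share of the tests that pass the gate, and the unconditional rate does not rise.

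**Conclusion.** The point holds in a limited form. SAP 14.2.1.10 contains an undefined, data-dependent condition that would be judged after unblinding and that the protocol does not have. The SAP does not settle whether it operates. A reader might infer that comparisons will be made only where a trend is seen; the unconditional statements in the same section prevent that conclusion.

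If the condition is applied, comparisons with placebo on a secondary objective are reported selectively. The size depends wholly on the gate, which the SAP does not give. The favourable gates illustrated give a mean reported difference of 0.36 to 0.77 SD when there is no effect, while a gate judged on an uncorrelated result gives no bias. If it is never applied, there is no selection. Primary PK conclusions are unaffected in either case. The sentence should be corrected because the ambiguity serves no purpose and removing it is nearly free.

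**What to change.** In SAP 14.2.1.10, replace the sentence that carries the trend condition with: *No formal hypothesis testing is planned; the exploratory comparisons listed below will be performed and reported for every listed endpoint whatever the observed result.* Do not substitute a numerical definition of trend, because that keeps the selection.

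In the same section, replace the sentence that leaves model details to model fit with: *The unstructured model will be fitted first; if it does not converge or its assumptions are doubtful, the fallback will be chosen without reference to the treatment effect, and the reason will be stated.* This keeps the legitimate concern with model assumptions and removes a second choice that could follow the result.

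These edits do not bring the SAP fully into line with Protocol 12.4.4.1 and 12.4.4.2. Other differences remain: SCTC-DI is tested by Wilcoxon, 5-D Itch has no between-group comparison, and the protocol's odds ratios are not mentioned. Those need separate handling.

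The cost is SAP wording and a few more tables where no trend is seen. No extra data are needed.

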2.2. SECONDARY OBJECTIVES AND ENDPOINTS

The secondary objectives are:

- To assess the safety and tolerability of oral FT011 compared to placebo in participants with diffuse SSc.
- To evaluate the short-term efficacy of oral FT011 compared to placebo in improving disease activity in participants with diffuse SSc.

Document: \$506df00529e1\$BDE32479744D47F0B3BAA4285D5BE091.docx

Author: ██████████

Version Number: Final v1.1

Version Date: 16Nov2022

Template No.: CS_TP_BS016 Revision 6

Reference: CS_WI_BS005

Effective Date: 02Dec2019

Copyright © 2009, 2010, 2012, 2016, 2018, 2019 IQVIA. All rights reserved. The contents of this document are confidential and proprietary to IQVIA Holdings Inc. and its subsidiaries. Unauthorized use, disclosure or reproduction is strictly prohibited.

The secondary endpoints are:

- Safety will be assessed by:
 - o Treatment-emergent adverse events from first dose of study drug to End of Study.
 - o Physical examination.
 - o Vital signs (blood pressure, heart rate, respiratory rate, and temperature).
 - o 12-lead electrocardiograms (ECG).
 - o Safety laboratory results (haematology, biochemistry, coagulation, and urinalysis).
 - o Use of concomitant medications.
- Efficacy will be assessed by:
 - o Change in modified Rodnan skin score (mRSS) from Baseline at each visit.
 - o Change in percent predicted forced vital capacity (FVC) from Baseline to Week 4, Week 8, and Week 12.
 - o Change in Scleroderma Health Assessment Questionnaire - Disability Index (SHAQ-DI) Score from Baseline to Week 4, Week 8, and Week 12.
 - o Change in Patient Global Assessment Score from Baseline to Week 4, Week 8, and Week 12.
 - o Change in Physician Global Assessment Score from Baseline to Week 4, Week 8, and Week 12.
 - o The proportion of patients showing an improvement (defined as ACR Composite Response Index in Diffuse Cutaneous Systemic Sclerosis (CRISS) score predicted probability of ≥ 0.60) at Week 12.
 - o Change in the Scleroderma Clinical Trials Consortium Damage Index (SCTC-DI) score from Baseline to Week 12.
 - o Change in the 5-D Itch Scale from Baseline to Week 12.

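### The example repeated-measures code adds an unstructured random-effects matrix to a residual variance, leaving one covariance parameter unidentified, and the SAP sets no rule for choosing another covariance structure

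*SAP*

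**What the plan says.** SAP 14.2.1.10 applies one mixed model for repeated measures to five endpoints: "For mRSS, percent predicted FVC, HAQ-DI, patient global assessment score, and physician global assessment score, the change from baseline values will be compared" between FT011 and placebo. The covariance is described as "participant as random effect using an unstructured covariance structure". Protocol 12.4.4.1 has nearly the same words: "subject as random effect with an unstructured covariance assumption".

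The example code gives the fixed effects and degrees-of-freedom method as "MODEL AVAL = TRT01P|VISIT BASELINE / DDFM = KENWARDROGER" and the covariance as "RANDOM VISIT / SUBJECT = SUBJID TYPE = UN". It has no REPEATED statement. The text after the code adds: "Details of model including covariance structure will be decided based on the model fit". It names no criterion, no list of candidate structures and no order.

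SAP 7.1 describes the model differently again. Its sentence can be read as making the visit-by-treatment interaction random along with participant, whereas the code has that interaction fixed.

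The visits come from SAP 2.2. Four of the endpoints follow the pattern "Change in percent predicted forced vital capacity (FVC) from Baseline to Week 4, Week 8, and Week 12". For the skin score the endpoint is "Change in modified Rodnan skin score (mRSS) from Baseline at each visit", and the schedule of assessments includes mRSS at Week 16.

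**The concern.** In PROC MIXED a RANDOM statement defines the between-participant matrix G, and the residual variance stays in the model unless a REPEATED statement replaces it. With TYPE=UN over visits, G alone can already reproduce any covariance matrix of the repeated measurements. The residual is then a surplus parameter, and the information matrix of the covariance parameters is singular for any data set with one record per participant per visit. Kenward-Roger inference uses the inverse of that matrix.

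What is at stake is control of the analysis more than the estimates. A warning caused by the code could lead the analyst to change the covariance structure, and the SAP does not say to what. SAP 4.3 places the final analysis after database lock and unblinding, so that choice could be made with results by arm in view. With about 10 participants per arm, the choice of structure can move standard errors noticeably.

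**Working it through.** The documents give no figure to reproduce here: there is no power calculation and no assumed SD.

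**Inputs from the documents.** Visits T = 3 (Weeks 4, 8, 12) for percent predicted FVC, HAQ-DI and the two global assessments. T = 4 for mRSS if Week 16 enters the model, which SAP 14.2.1.10 does not state. About 30 participants, 10 per arm. Two-sided 5% level.

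**Assumptions.** One record per participant per visit in the model data set. SAP 6.7 excludes unscheduled values from by-visit summaries but does not say so for the model.

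**1. Parameter count.** The code implies V = G + σ²I, where V is the covariance of one participant's T values. For any small c, replacing G by G + cI and σ² by σ² − c leaves V, and hence the likelihood, unchanged.

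| | T = 3 | T = 4 |
|---|---|---|
| Distinct elements of V, T(T+1)/2 | 6 | 10 |
| Parameters in the code, T(T+1)/2 + 1 | 7 | 11 |
| Surplus | 1 | 1 |

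**2. Numerical check.** Data were simulated for 3 × 10 participants with an assumed SD of 5 and correlation 0.5, both with complete data and with one participant per arm missing the last visit.

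- Rank of the REML information matrix: 6 of 7 (T = 3) and 10 of 11 (T = 4). With a REPEATED unstructured matrix the ranks are 6 of 6 and 10 of 10.
- −2 REML log-likelihood for T = 3, complete data: 313.485 at σ² = 0, 1.741, 3.482 and 6.268.
- −2 REML log-likelihood for T = 4, complete data: 421.705 at σ² = 0, 0.965, 1.931 and 3.475.
- The missing-data cases are equally flat.

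**3. Effect on the treatment comparison.** For the Week 12 difference, complete data, using a generalised inverse for the singular form:

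| | Estimate | Kenward-Roger SE | df |
|---|---|---|---|
| T = 3, REPEATED UN | 0.3772 | 1.81866 | 26.20 |
| T = 3, RANDOM UN + residual | 0.3772 | 1.81866 | 26.20 |
| T = 4, REPEATED UN | −1.6677 | 1.60925 | 26.04 |
| T = 4, RANDOM UN + residual | −1.6677 | 1.60925 | 26.04 |

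The degrees of freedom are a Satterthwaite-type calculation. Only the split between G and σ² is lost.

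**4. Effect of a different structure.** Rejection of a true null at Week 12 was simulated with four visits, complete data and 27 residual df. Tests used 27 or 50 df as approximations.

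First simulation: assumed SDs of change rising from 2.5-3 to 5; 700 runs; Monte Carlo SE about 1 percentage point.

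| Analysis | Null rejection |
|---|---|
| Unstructured | 3-6% |
| Structure chosen by AIC | 3-6% |
| Compound symmetry or AR(1) imposed | 7-10% |
| Most favourable of five structures | 7-10% |

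Second simulation: compound symmetry imposed, correlations 0.3-0.7, 4000 runs.

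| SDs over the four visits | Null rejection |
|---|---|
| Equal | 4.2-4.9% |
| 4, 4.5, 5, 5 (mild rise) | 6.4-7.4% |
| Steep rise | 8-11% |

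A hand check of the mild case, ignoring the baseline covariate: compound symmetry pools the variances to (16 + 20.25 + 25 + 25)/4 = 21.5625, against a true Week 12 variance of 25. The SE is therefore multiplied by √(21.5625/25) = 0.929. At 27 df the effective critical value falls from 2.052 to 1.906, which gives a rejection rate of about 6.7%, in line with the simulation.

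**The case against.** The strongest reply is that no result is lost. Step 3 supports this: V, the treatment difference, its standard error and its df do not depend on how the variance is split. A reader might infer from the singular matrix that the estimates are biased, or that the model cannot be fitted at all. The documents and the calculations support neither. No SAS run was made, so a warning or non-convergence is possible but unobserved; a harmless Hessian message would fit the same evidence.

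Second, the code is labelled an example, and the prose names a repeated-measures model with unstructured covariance, which is estimable. A programmer could write REPEATED without departing from that intent. This stands in part, but the prose also calls participant a random effect, which points back to RANDOM, and no other operational specification is given.

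Third, the sentence on model fit applies whether or not the code is corrected, so the two issues are separate. Choosing by fit also does not by itself inflate error: AIC selection stayed at 3-6%. A reader might take 7-11% as the error rate of the plan as written. It is not. Those rates need a homogeneous structure imposed on unequal variances, or selection of the most favourable p-value, and they rest on SDs that the documents do not give. What remains is that the SAP does not say what counts as fit.

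Fourth, Protocol 12 gives the SAP precedence, so loosening the covariance is permitted. However, SAP 3.3 lists two changes from the protocol and this is not one of them.

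Fifth, the primary endpoints are pharmacokinetic. SAP 14.2 calls the efficacy comparisons exploratory, with no formal hypothesis testing. This stands and limits the weight of the point.

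**Conclusion.** The code is over-parameterised by exactly one covariance parameter for all five endpoints, given one record per participant per visit; replicate records would remove the problem. The count of 11 against 10 for mRSS also assumes that Week 16 is modelled. On convergence the inference is the same as from a correctly coded unstructured model, so the direct effect on estimates, intervals and p-values is nil.

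The practical weakness is that a possible code-induced warning sits beside an open choice of covariance structure after unblinding, where the protocol had specified unstructured. The possible cost is a null rejection rate of about 7% with a mild rise in variance and up to 11% with a steep one, if a homogeneous structure is imposed. There is no visible cost if selection is honestly by AIC. Because these are exploratory comparisons of secondary endpoints, the correction is worth making for its low price but is not a must-fix.

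**What to change.** 1. In SAP 14.2.1.10 replace the RANDOM line with `REPEATED VISIT / SUBJECT=SUBJID TYPE=UN;`.
2. Replace the sentence that leaves model details to fit with a fixed rule. Unstructured is final unless it fails to converge. In that case use the first structure that converges from a pre-specified ordered list with visit-specific variances, keeping the same fixed effects. Heterogeneous Toeplitz, then ARH(1), then heterogeneous compound symmetry is one reasonable order; having an order matters more than which one.
3. In SAP 7.1 and 14.2.1.10 drop the random-effect wording. State baseline as covariate, fixed effects for treatment, visit and treatment-by-visit, and an unstructured within-participant covariance.

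The cost is one line of code and a few sentences of SAP text, with no change to data collection.
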